4.2 CH505TF gp120

The CH505TF gp120 to be used in this study was derived from the clade C transmitted/founder virus which was isolated from a single acutely HIV-1—infected donor from Malawi (CH505) (14, 30, 31). CH505TF was chosen based on its binding affinity to the CH103 bnAb lineage as shown in Table 4-1. CH505TF binds with high affinity to the unmutated common ancestor (UCA) of the CH103 lineage (30).

The CH505TF gp120 immunogen has an N-terminal deletion to facilitate production by decreasing protein dimer formation and increasing production yield (30). CH505TF is currently being evaluated in combination with GLA-SE in adult participants in HVTN 115.

Table 4-1 Binding of CH103 lineage antibodies to autologous CH505 Envs. Choice of transmitted/founder CH505 Env by binding EC_{50} levels to recombinant sequential CH505 Envs. Data are in EC_{50} binding titers in ELISA. (Red shading highlights the antigens being assessed in HVTN 115 and the antibodies they bind to.)

	Binding of CH103 lineage antibodies to the autologous CH0505 Env, EC50, ug/ml													
Antigen	UCA	IA8	IA7	IA6	IA5	IA4	IA3	IA2	IA1	CH105	CH103	CH104	CH106	
CH0505 TFD8gp120	2.116	1.277	0.412	0.534	0.254	0.133	0.177	0.147	0.179	0.194	0.095	0.138	0.086	
CH0505 TF gp140C	4.714	1.931	0.402	0.536	0.203	0.164	0.132	0.111	0.122	0.130	0.072	0.180	0.073	
CH505.s.03.D8.gp120	23.184	1.870	>100	0.525	0.236	0.266	0.126	0.189	0.218	0.192	0.078	0.218	0.097	
CH505.s.03.gp140C	2.732	0.849	5.439	0.299	0.223	0.770	0.107	0.083	0.093	0.095	0.059	0.087	0.058	
CH505.08.D11gp120	>100	3.116	0.973	1.837	1.504	>100	0.473	0.746	0.633	0.387	0.452	0.613	0.271	
CH505.08.gp140C	>100	1.745	>100	2.245	0.578	0.324	0.401	0.307	0.487	0.560	0.335	0.483	0.266	
CH505.30.e6 gp140	NB	NB	2.212	>100	0.597	>100	0.320	0.286	0.281	0.296	0.158	0.274	0.181	
H0505.w30.23 D8 gp120	NB	NB	NB	>100	>100	NB	0.360	0.248	0.356	0.399	0.123	0.402	0.217	
CH0505.w30.23gp140C	NB	NB	>100	7.029	0.196	6.689	0.132	0.108	0.127	0.125	0.067	0.110	0.081	
CH505 W53.e16.D8 gp120	NB	NB	NB	NB	>100	NB	0.171	0.092	0.126	0.162	0.038	0.101	0.074	
CH505.w53.e16.gp140C	NB	NB	NB	NB	>100	NB	0.141	0.081	0.103	0.132	0.046	0.090	0.069	
CH505.w78.1.D8.gp120	NB	NB	NB	NB	NB	NB	0.779	0.359	0.498	0.774	0.067	0.449	0.652	
CH505.w78.1.gp140C	>100	NB	NB	NB	NB	NB	0.528	0.263	0.339	0.480	0.110	0.344	0.589	
CH505.w78.7.D8.gp120	NB	NB	NB	NB	NB	NB	0.233	0.119	0.164	0.198	0.047	0.211	0.240	
cH505.w78.7.gp140C	NB	NB	NB	NB	NB	NB	0.179	0.284	0.151	0.167	0.055	0.140	0.210	
CH505.w78.16.D8gp140	NB	NB	NB	NB	NB	NB	2.689	0.217	0.292	0.507	0.071	0.302	0.248	
CH505.w78.16.gp140C	NB	NB	NB	NB	NB	NB	1.220	0.276	0.336	0.492	0.089	0.349	0.193	
CH505.w78.25.D8.gp120	NB	NB	NB	NB	NB	NB	1.332	0.499	0.767	1.179	0.125	0.655	0.480	
CH505.w78.25.gp140C	NB	NB	NB	NB	NB	NB	0.515	0.405	0.317	0.374	0.102	0.266	0.197	
CH505.w78.33.D8.gp120	NB	NB	NB	NB	NB	NB	0.086	0.090	0.096	0.125	0.041	0.121	0.088	
CH505.w78.33.gp140C	NB	NB	NB	NB	NB	NB	0.100	0.053	0.062	0.085	0.036	0.058	0.047	
CH505.w78.38.D8.gp120	NB	NB	NB	NB	>100	NB	>100	0.709	0.867	1.182	0.219	0.797	0.589	
CH505.w78.38.gpc140C	NB	NB	NB	NB	>100	NB	>100	>100	>100	>100	0.724	>100	0.716	
CH505_w100.A4.D8.gp120	NB	NB	NB	NB	>100	NB	0.238	0.074	0.097	0.149	0.028	0.164	0.074	
CH505.w100.A4.gp140c	NB	NB	NB	NB	>100	NB	0.789	1.164	0.326	0.491	0.122	0.422	0.248	
CH505.w100.B6.D8.gp120	NB	NB	NB	NB	NB	NB	0.101	0.024	0.035	0.068	0.583	0.031	0.046	
CH505.w100.B6.gp140C	NB	NB	NB	NB	NB	NB	0.026	0.015	0.016	0.023	0.110	0.016	0.018	

4.3 GLA-SE adjuvant

To compare immunogenicity results between infants immunized with CH505TF gp120 and adults in HVTN 115, this study will use the same adjuvant system.

GLA-SE is a synthetic TLR4 agonist formulated in a stable nano-emulsion of squalene oil and promotes a robust Th1-type immune response to vaccine antigens (32, 33). GLA-SE has been tested in over 2500 individuals in phase 1, 2 and 3 trials with a variety of antigens. No significant safety concerns were reported. Previous clinical trial experience with GLA-SE and other antigens in adults is described in Section 4.8.2. Two trials are underway in children evaluating GLA-SE with other vaccines: a protein subunit vacine for schistosomiasis (NCT03799510), and a tuberculosis vaccine (NCT03806699). Our study will further compliment these studies in elucidating the safety and tolerability of this adjuvant in combination with other vaccines in infants. Importantly, the Th1-type immune response elicited is of interest in this population because of potential benefit towards more rapid cellular responses and more rapid bnAb development.

A study in infant rhesus macaques testing HIV-1 Env bivalent clade C gp120 C1086 and gp120 TV1 evaluated various adjuvants including GLA-SE at the dose as proposed in this study. This adjuvant demonstrated good immunogenicity in these infants, which weigh on average 500 g, indicating the immunogenicity of this dose in low-weight NHPs. GLA-SE adjuvanted vaccines has been previously studied in more than 2500 human adults and these GLA-SE adjuvanted vaccines have been demonstrated to be safe (see Table 4-7). Moreover, no major safety signal has been observed in adults who received a GLA-SE adjuvated gp120 vaccine in the Part A of HVTN 115.

4.4 Trial design rationale

An important goal for the vaccine field is to evaluate the concept of inducing broadly neutralizing antibodies against HIV-1. This study complements the work done in adults that evaluates a series of immunogens that, in an NHP model, were found to be capable of recreating the natural evolution of Env that promotes CD4bs specific antibody evolution. We will provide key insight into whether the infant immune milieu is more supportive of the development of several classes of affinity matured, somatically hypermutated bnAbs than the adult immune system, with important biological implications for the development of a generally effective HIV vaccine. In addition, we will also assess whether the promising adjuvant GLA-SE is as safe and tolerable in an infant population as it has been in adult populations.

It is critical to evaluate whether repeated administrations of GLA-SE with a single protein are safe in a neonatal population and do not interfere with required EPI vaccinations (secondary endpoint 1). This study will lay the groundwork for subsequent testing with sequential immunogens (eg, more directed lineage shaping approach, such as in HVTN 115 Part B), which will likely require a larger number of participants. All currently envisioned testing regimens require five (or more) doses of vaccine product. By including five doses with a placebo group powered for a robust consideration of safety, the study will allow for assessment of whether five doses of a GLA-SE adjuvanted vaccine is safe in infants. In

addition, the measurement of EPI vaccine responses after one year of vaccination will provide additional insight on whether GLA-SE causes interference with other important vaccines, as "bystander" interference has been observed with prior neonatal vaccination approaches (34).

The use of a placebo arm does not compromise standard of care for either the mother or the infant as both groups will receive the local standard of care for prevention of HIV transmission through breastfeeding.

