4.4.6 Choice of control

Sodium Chloride for Injection, 0.9% will be used as placebo.

Inclusion of placebo groups in this study is deemed necessary to maintain blinding when evaluating clinical events and their relationship to study vaccine. In addition, comparisons of safety and immunogenicity data between vaccine and placebo recipients could provide useful descriptive results despite the small sample size.

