6.1 Accrual and sample size calculations

Recruitment will target enrolling 38 healthy, HIV-uninfected infant participants born by Caesarian section to HIV-infected mothers (HIV exposed, uninfected infants). Although this study is proposed to be a direct comparison with HVTN 115, there are important differences in the populations that justify the inclusion of a larger placebo group. Specifically, we anticipate a higher rate of background severe adverse events in this population, as previous vaccine studies have determined a rate of 18% SAE in the placebo arm (74). This is markedly different from the background rate of severe adverse events in typical HVTN adult studies (~1-2%), supported by emerging safety data from the HVTN 115 study in adults (see Section 4.8.1). Therefore, we propose including a larger placebo group to ensure capacity for determining a safety signal in this vulnerable population.

There are both technical and logistical considerations that favor enrolling infants delivered via Caesarian section. From a technical standpoint, assessment of the evolution of antibodies requires an understanding of the baseline nature of B cells prior to vaccination. Standard assessment of antigen-specific B cell lineages requires several milliliters of blood, a volume that is unsafe in neonates. We intend to protect the participants of the study by performing baseline cellular assays on cord blood that would otherwise be discarded. For logistical reasons related to the study site, cord blood can only be collected during Caesarian sections.

Since enrollment of mother-infant pairs is concurrent with infants receiving the first study vaccination, all participants will be included in the safety analysis. However, for immunogenicity analyses, it is possible that data may be missing for various reasons, such as participants terminating from the study early, problems in shipping specimens, low cell viability of processed peripheral blood mononuclear cells (PBMCs), or high assay background. While the site staff report a historical rate of 10% missingness in infant studies conducted at the site, immunogenicity data from previous phase 1 and 1 phase 2a HVTN trials indicate that 25% is a reasonable estimate for the rate of missing data for the later timepoint (1 year). For this reason, the sample size calculations below account for 25% of enrolled participants having missing data for the primary immunogenicity endpoint.

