6.1.1 Sample size calculations for safety

The goal of the safety evaluation for this study is to identify safety concerns associated with product administration. The ability of the study to identify SAEs can be expressed by the true event rate above which at least 1 event would likely be observed and the true event rate below which no events would likely be observed. Specifically, in the pooled Groups 3 and 5 (20 mcg CH505TF gp120 + 5 mcg GLA-SE vaccine arms) of the study (n = 18), there is 90% chance of

observing at least one event, if the true rate is 12% or more, and there is a 90% chance of observing no events, if the true rate is 0.58% or less. In the pooled placebo group of the study (n = 10), there is 90% chance of observing at least one event, if the true rate is 20% or more. There is a 90% chance of observing no events, if the true rate is 1% or less.

As a reference, in HVTN vaccine trials in Southern Africa from April 2008 through March 2018, about 1.7% of adult participants who received placebos experienced an SAE. Based on recent infant clinical trial studies including infants at the PHRU site, approximately 18% of infant participants who received placebos experienced an SAE (54).

Binomial probabilities of observing 0, 1 or more, and 2 or more events among arms of size 18 and 10 are presented in Table 6-1 for a range of possible true adverse event rates. These calculations provide a more complete picture of the sensitivity of this study design to identify potential safety problems with the vaccine.

Table 6-1 Probability (Pr) of observing 0 events, 1 or more events, and 2 or more events, among arms of size 18 and 10, for different true event rates

True event rate (%)	Pr(0/18)	Pr(1+/18)	Pr(2+/18)	Pr(0/10)	Pr(1+/10)	Pr(2+/10)
1	83.5	16.5	1.4	90.4	9.6	0.4
5	39.7	60.3	22.6	59.9	40.1	8.6
10	15	85	55	34.9	65.1	26.4
20	1.8	98.2	90.1	10.7	89.3	62.4
30	0.2	99.8	98.6	2.8	97.2	85.1
40	0	100	99.9	0.6	99.4	95.4
50	0	100	100	0.1	99.9	98.9
60	0	100	100	0	100	99.8
70	0	100	100	0	100	100
80	0	100	100	0	100	100
90	0	100	100	0	100	100

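### Sections 4.4 and 6.1 credit the placebo group with power to determine a safety signal, but only within-arm figures are given and, for all-cause SAEs, 10 placebo infants support description only

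*Protocol*

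**What the plan says.** Protocol 4.4 (Trial design rationale) supports the five-dose design partly by "a placebo group powered for a robust consideration of safety". Protocol 6.1 gives the reason for the group's size. It first reports that "previous vaccine studies have determined a rate of 18% SAE in the placebo arm", contrasts this with about 1% to 2% in the network's adult studies, and concludes: "we propose including a larger placebo group to ensure capacity for determining a safety signal in this vulnerable population".

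Protocol 6.1.1 then gives the safety operating characteristics, all within one arm:
- the true rates at which at least one event, or none, is likely; for the 10 placebo infants, "there is 90% chance of observing at least one event, if the true rate is 20% or more";
- Table 6-1, the probability of 0, 1 or more, and 2 or more events for arms of 18 and 10;
- Table 6-2, score 95% intervals for each observed count in an arm of 18 or 10.

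The same section repeats that "approximately 18% of infant participants who received placebos experienced an SAE".

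Other sections set a lower aim. Protocol 4.4.6 says that placebo comparisons "could provide useful descriptive results despite the small sample size". Protocol 6.4.3.2 and SAP 8.3.2 plan no formal test of AEs between arms. Protocol 6.1.2 says openly that power is low for the vaccine-placebo comparison of immunogenicity response rates. No matching statement is made for safety.

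**The concern.** Power, and the capacity to determine a signal over an 18% background, are properties of a comparison between arms. The documents state them without a between-arm figure and elsewhere say that the comparison is descriptive. Safety is primary objective 1, the participants are newborns, and the 18% rate is the stated reason for the number of placebo infants. An ethics committee or a later reader could therefore give a finding of similar SAE rates more weight than 10 placebo infants can carry.

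The second difficulty is how 6.1.1 describes the ability to identify SAEs. The chance of seeing at least one event is a useful yardstick when the event hardly ever occurs without the vaccine. At an 18% background it is close to certain with a harmless vaccine.

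**Working it through.** **Inputs.** Placebo SAE rate 18% (6.1 and 6.1.1; the two sections cite different references for it, and the figure is taken as given). Placebo n = 10 and pooled Groups 3 and 5 n = 18 (6.1.1). All vaccinees n = 28 (Table 3-1). No loss for safety, since 6.1 includes every enrolled infant.

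**Assumptions not in the documents.** Two-sided Fisher's exact test at 5%, borrowed from the immunogenicity power statement in 6.1.2 because no SAE test is planned. A doubling of the SAE rate, 18% to 36%, as an illustrative effect.

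**1. The plan's own figures.** The rate giving a 90% chance of at least one event is 1 - 0.1^(1/n): 12.0% for n = 18 and 20.6% for n = 10. The rate giving a 90% chance of none is 1 - 0.9^(1/n): 0.58% and 1.05%. The plan states 12%, 20%, 0.58% and 1%, so these reproduce to rounding. At exactly 20%, 1 - 0.8^10 = 89.3%, as in Table 6-1.

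**2. At least one SAE with no vaccine effect.** P = 1 - 0.82^n.
- n = 10: 86%
- n = 18: 97%
- n = 28: 99.6%

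Table 6-1 shows the same in its 20% row (98.2% for 18, 89.3% for 10). In its 1% row the value for 18 infants is 16.5%, and there the yardstick does carry information.

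**3. Between-arm power.** Sum, over all counts x among vaccinees and y among placebos, Bin(x; n, p1) × Bin(y; 10, 0.18) for every table with Fisher p ≤ 0.05.

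| Vaccinee SAE rate | 18 vs 10 | 28 vs 10 |
|---|---|---|
| 36% (doubling) | 11.9% | 9.4% |
| 54% (tripling) | 42% | 38% |
| Rate giving 80% power | 72.6% | 70.9% |

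With 2/10 placebo SAEs, significance needs at least 12/18 or 18/28 among vaccinees.

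**4. Sensitivity to the test.** Power for a doubling, then the rate giving 80% power:
- one-sided Fisher at 5%: 15.0% and 70.4% (18 vs 10); 15.7% and 66.4% (28 vs 10)
- Barnard-type unconditional test: 15.1% and 70.4%; 15.4% and 67.8%
- normal approximation: 14.9% and 70.5%; 15.4% and 67%

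Over all variants, power for a doubling is about 9% to 16%, and 80% power needs a vaccinee rate of about 66% to 73%.

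**5. Precision, with no test assumed.** The Newcombe interval combines the score limits (l, u) of each arm: d - √[(p1-l1)² + (u2-p2)²] to d + √[(u1-p1)² + (p2-l2)²].

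Take 3/18 vs 2/10, counts close to 18% in both arms. From Table 6-2 the limits are 5.8% to 39.2% and 5.7% to 51.0%, and d = 16.7 - 20.0 = -3.3 points.
- Lower: -3.3 - √(10.8² + 31.0²) = -36 points
- Upper: -3.3 + √(22.6² + 14.3²) = +23 points

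For 5/28 vs 2/10 the interval is -35 to +21 points. The widths are about 60 and 55 points.

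**The case against.** **No SAE test is planned, so power is the wrong measure.** This stands as a limit on step 3, where the figures describe a hypothetical test. It does not rescue the wording, because a group cannot be powered for a comparison that is not to be tested. Step 5 makes the point with no test at all.

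**The imprecision is disclosed.** In part. Tables 6-1 and 6-2 go beyond the chance of at least one event: they give the chances of none and of two or more, and per-arm intervals that are visibly wide. A reader might infer that the at-least-one-event figure is all that the protocol offers, and that would be wrong. What is missing is any figure for the difference between arms.

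**Safety is wider than all-cause SAEs.** This stands. Primary endpoint 1 also covers reactogenicity, laboratory measures and weight gain, and reactogenicity severity is tested between arms (6.4.3.1). SAE monitoring does not rest on a test between arms: relatedness is assessed, a related SAE triggers an immediate pause (Table 11-3), and the Safety Monitoring Board reviews unblinded data about every 4 months (11.1.2). A reader might infer from the low power that harm would go unnoticed. The documents do not support that, because a non-significant all-cause comparison is not the only route to detection.

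**The placebo group is in fact larger.** It is, relative to the adult trial: 10 of 38 here against 6 of 42 in HVTN 115 Part A (Table 4-6). The comparative word is accurate. The capacity attributed to it is what lacks support.

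**Phase 1 trials are not powered for safety.** Agreed, and that is the reason to remove the claim. A reader might infer that the sample size is wrong or that a calculation failed. Neither follows: the stated within-arm figures checked are correct, and a descriptive comparison of this size is what 4.4.6 and 6.4.3.2 describe.

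**Conclusion.** The point holds as a mismatch between the stated rationale and what the design can deliver. The wording in 4.4 and 6.1 has no between-arm figure behind it and conflicts with 4.4.6 and 6.4.3.2.

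For all-cause SAEs the gap is large. The 9% to 16% power for a doubling rests on an 18% placebo rate, an assumed test at 5% and an illustrative effect. The lowest value belongs to two-sided Fisher with all 28 vaccinees pooled; with the groups that the protocol itself pools it is 12%. The interval widths need only the background rate and the arm sizes, and they lead to the same conclusion. The at-least-one-event figures are arithmetically right but do not indicate a vaccine signal for an outcome this common at background.

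The finding does not extend to reactogenicity, to rare event types or to the safety monitoring rules.

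**What to change.** 1. In Protocol 4.4 and 6.1, replace the claims of power and of capacity to determine a safety signal with a statement that the placebo group is included to maintain blinding and for descriptive comparison. This agrees with 4.4.6 and 6.4.3.2.
2. In 6.1.1, add the expected vaccine-minus-placebo 95% interval at an 18% background, for example 3/18 vs 2/10: about -36 to +23 points. If a detectable rate is also given, state its assumptions: 18% placebo rate, two-sided Fisher at 5%, about 73% for 18 vs 10 and 71% for 28 vs 10.
3. In 6.1.1, state that the at-least-one-event figures are informative for event types that are rare at background and not for all-cause SAEs.

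The cost is a few sentences and one line of figures, and a less favourable description of the safety comparison. No infants are added, and the planned analyses and safety monitoring do not change.

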4.4.1 Study Population

HIV exposed infants represent the population that may potentially benefit from this vaccine approach. Our overall objective is to evaluate interventions that substantially reduce the risk of HIV-1 transmission through breastmilk, hence the use of this population of HIV-exposed, uninfected infants.

4.4.2 Cord Blood

To minimize blood draws and to optimize our understanding of cellular responses, we will be using cord blood to evaluate baseline immunogenicity. Without the use of cord blood, some of the baseline immunologic studies we are proposing would require volumes of blood that would be unsafe to draw directly from neonates. For logistical reasons, cord blood can only reliably be obtained during planned Caesarian sections and planned Caesarian sections occur more frequently in this population. We will only enroll women who will require a planned Caesarian section, as determined by their obstetrical care provider.

4.4.3 Immunization number

Several interlinked considerations have informed the design of our study, utilizing five immunizations of CH505TF gp120 starting at birth, with the primary immunogenicity analysis at one year. These include: 1) to begin vaccination at birth to engage the unique qualities of the neonatal immune system, 2) the need to test for infant antibody responses at a timepoint where maternal antibodies have waned, and 3) to compare the infant immune response to the adult immune response in HVTN 115.

4.4.4 Dose (amount and number)

The intention of this study is to evaluate the safety and immunogenicity of CH505TF gp120 adjuvanted with GLA-SE in infants and to compare these data to the findings of the adult HVTN 115 study using the same adjuvanted vaccine formulation. In this study, HEU infants will be enrolled within 5 days of birth to receive vaccination with the CH505TF gp120 immunogen adjuvanted with GLA-SE or placebo. The highest GLA-SE dose (5 mcg) chosen for this study is supported by data coming from a nonhuman primate study that demonstrated the immunogenicity of GLA-SE in infant rhesus macaques (35). It is important to note that this is half the dose of GLA-SE administered to adults in the HVTN 115

study. This is consistent with the approach for vaccines licensed for use in pediatric populations such as Hepatitis A and Hepatitis B, both of which use half the adult dose in children. We aim to do a dose escalation for the adjuvant, starting with a lower 2.5 mcg GLA-SE dose in a small number of infants, use a planned enrollment hold to review safety data from these infants, and then increase to the 5 mcg GLA-SE dose with an additional enrollment hold for PSRT review of safety data.

There are HIV-specific concerns regarding somatic hypermutation, a necessary but not sufficient element for driving a bnAb response, that support the 5 mcg dose. In preclinical studies of other adjuvants (cholera toxin A1-DD and deltainulin), increasing the dose of adjuvant is clearly associated with increasing somatic hypermutation (36, 37). Insufficient TLR4 stimulation (the target of GLA-SE) has been demonstrated to mediate the poor affinity maturation and lack of germinal center responses observed with formalin-inactivated RSV vaccines (38). In addition, pre-clinical data would suggest that there is likely to be less reactogenicity in infants to the GLA-SE adjuvant. In vitro studies have demonstrated that both neonatal and infant whole blood stimulated with GLA produces reduced amounts of the pyrogens TNF, IL-12 (p40), and IFN-γ when compared to adult blood (39). These inflammatory cytokines are likely mediators of reactogenicity (40).

The immunogen dose is the lowest dose (20 mcg) of CH505TF gp120 evaluated in HVTN 115 Part A. In HVTN 115 Part A, there were no statistically significant differences in magnitude of elicited antibodies or in response rates between the 20 mcg, 100 mcg, and 400 mcg dosing groups. In the adult cohort, no suppressive effect was seen with higher protein doses in HVTN 115 Part A; however, consistent with other vaccines used in both adult and infant populations, we have elected to use the lower 20 mcg dose to reduce the risk of high-dose suppression. It is possible that we may observe interference from maternal polyclonal antibodies vertically transferred to the infant; given the proven efficacy of EPI vaccines in this population where similar maternal antibody interference could occur, we believe the dose of 20 mcg offers the best balance between safety and immunogenicity.

In addition to the 20 mcg dose of CH505TF gp120, we propose to include a 5 mcg arm to further explore immunogenicity of CH505TF gp120 recombinant protein. This choice is supported both by preclinical studies of CH505TF gp120 and by the results of HVTN 115 Part A. As described below in Section 4.7.3, we performed a dose ranging study in rhesus macaques. After the second and third immunizations, neutralization titers were similar in all dose groups (5 to 600 mcg/dose; Figure 4-2).

[figure not shown]

Figure 4-2 Neutralization activity elicited by CH505TF gp120 immunization against three isolates in the TZM-bl assay. There are no statistically significant differences between groups.

In HVTN 115 Part A, the frequency of antigen-specific B cells in peripheral blood after the fifth dose of vaccine was similar in all groups, with a slightly higher frequency and response rate observed in the higher dose groups compared with the 20 mcg/dose group. In this pediatric study, the selection of lower doses is consistent with vaccine strategies for other pathogens where lower doses are often used. While this study will not be powered for a formal comparison between these arms, previous pediatric vaccine studies have demonstrated that immune responses induced by a lower dose of protein were comparable to or greater than those seen with the higher dose. In the malaria RTS,S vaccine regimen, a delayed fractional immunogen dose equal to 20 mcg induced higher antibody avidity and antibody somatic hypermutation as compared to the higher dose (41). The inclusion of the 5 mcg dose in this study will permit a comparison of antibody avidity with the 20 mcg dose in infants and with all doses (20, 100 and 400 mcg) in adult immune responses from the HVTN 115 study.

The inclusion of five doses of a single product with a placebo arm will allow for directly assessing safety and testing whether the neonatal immune system has characteristics favorable to lineage-directed vaccination strategies.

